10.4 Appendix 4: Contraceptive guidance and collection of pregnancy information

Definitions

Woman of childbearing potential (WOCBP)

A woman is considered fertile following menarche and until becoming postmenopausal unless permanently sterile (see below).

Women in the following categories **are not considered WOCBP**:

1. Premenarchal
2. Premenopausal female with 1 of the following:
 - Documented hysterectomy
 - Documented bilateral salpingectomy
 - Documented bilateral oophorectomy
3. Postmenopausal female
 - A postmenopausal state is defined as no menses for 12 months without an alternative medical cause. A high follicle-stimulating hormone (FSH) level in the postmenopausal range may be used to confirm a postmenopausal state in women not using hormonal contraception or hormonal replacement therapy (HRT). However, in the absence of 12 months of amenorrhea, a single FSH measurement is insufficient.
 - Females on HRT and whose menopausal status is in doubt will be required to use one of the non-estrogen hormonal highly effective contraception methods if they wish to continue their HRT during the study. Otherwise, they must discontinue HRT to allow confirmation of postmenopausal status before study enrollment.

Contraception guidance

Female participants

Female study participants of childbearing potential are eligible to participate if they agree to use a highly effective method of contraception consistently and correctly as described in the table below.

Table 10-1: Highly effective contraceptive methods^a

Highly effective contraceptive methods that are user dependent^b
Failure rate of <1% per year when used consistently and correctly.
Combined (estrogen and progestogen containing) hormonal contraception associated with inhibition of ovulation 
• Oral• Intravaginal• Transdermal
Progestogen only hormonal contraception associated with inhibition of ovulation 
• Oral• Injectable
Highly effective methods that are user independent^c
Implantable progestogen only hormonal contraception associated with inhibition of ovulation 
• Intrauterine device (IUD)• Intrauterine hormone-releasing system (IUS)• Bilateral tubal occlusion
Vasectomized partner
A vasectomized partner is a highly effective contraception method provided that the partner is the sole male sexual partner of the WOCBP and the absence of sperm has been confirmed. If not, an additional highly effective method of contraception should be used.
Sexual abstinence
Sexual abstinence is considered a highly effective method only if defined as refraining from heterosexual intercourse during the entire period of risk associated with the study medication. The reliability of sexual abstinence needs to be evaluated in relation to the duration of the study and the preferred and usual lifestyle of the study participant.
NOTES:
a) In case of newly started contraception pills/IUDs, the investigator should consider the correct timing of starting/applying such methods in relation to the menstrual cycle and the manufacturing instruction as when these newly started methods would become effective.
b) Typical use failure rates may differ from those when used consistently and correctly. Use should be consistent with local regulations regarding the use of contraceptive methods for study participants participating in clinical studies.

Pregnancy testing

- WOCBP should only be included after a confirmed menstrual period and a negative highly sensitive serum pregnancy test.
- Additional pregnancy testing should be performed as specified in the Schedule of Activities (Section 1.3) and as required locally.
- Pregnancy testing will be performed whenever a menstrual cycle is missed or when pregnancy is otherwise suspected.
- Pregnancy testing, with a sensitivity of 25mIU/mL will be performed.

Female participants who become pregnant

- Any female study participant who becomes pregnant while participating in the study will be withdrawn from the study.
- The investigator will collect pregnancy information on any female study participant who becomes pregnant while participating in this study. Information will be recorded on the appropriate form and submitted to the sponsor within 24 hours of learning of a study participant's pregnancy. The study participant will be followed to determine the outcome of the pregnancy. The investigator will collect follow-up information on the study participant and the neonate and the information will be forwarded to the sponsor. Generally, the follow-up will be at least 12 months after the delivery date. Any termination of pregnancy will be reported, regardless of fetal status (presence or absence of anomalies) or indication for the procedure.
- While pregnancy itself is not considered to be an AE or SAE, any pregnancy complication or elective termination of a pregnancy will be reported as an AE or SAE. A spontaneous abortion is always considered to be an SAE and will be reported as such. Any post-study pregnancy-related SAE considered reasonably related to the study medication by the investigator will be reported to the sponsor as described in Section 8.3.5. While the investigator is not obligated to actively seek this information in former study participants, he or she may learn of an SAE through spontaneous reporting.

Male Participants With Partners Who Become Pregnant

- The investigator will attempt to collect pregnancy information on any male participant's female partner who becomes pregnant while the male participant is in this study. This applies only to male participants who receive rozanolixizumab. If the participant is later found to be on placebo, then pregnancy data collection can stop.
- After obtaining the necessary signed informed consent from the pregnant female partner directly, the investigator will record pregnancy information on the appropriate form and submit it to the sponsor within one working day of learning of the partner's pregnancy. The female partner will also be followed to determine the outcome of the pregnancy. Information on the status of the mother and child will be forwarded to the sponsor. Generally, the follow-up will be at least 12 months after the delivery date. Any termination of the pregnancy will be reported regardless of fetal status (presence or absence of anomalies) or indication for the procedure.

10.5 Appendix 5: Genetics

Use and analysis of DNA

- Genetic variation may impact a study participant's response to study medication, susceptibility to, and severity and progression of disease. Variable response to study medication may be due to genetic determinants that impact drug absorption, distribution, metabolism, and excretion; mechanism of action of the drug; disease etiology; and/or molecular subtype of the disease being treated. Therefore, where local regulations and IEC allow, a blood sample will be collected for DNA analysis from consenting study participants.
- DNA samples will be used for research related to rozanolixizumab and/or FMS and related diseases. They may also be used to develop tests/assays, including diagnostic tests related to rozanolixizumab /or interventions of this drug class and FMS. Genetic research may consist of the analysis of one or more candidate genes or the analysis of genetic markers across the entire genome (as appropriate), but only as they relate to the aims of further understanding the response to rozanolixizumab and FMS.
- The samples may be analyzed as part of this study alone or as part of a multi-study assessment of genetic factors involved in FMS and the response to rozanolixizumab or study medications of this class, and to understand the disease or related conditions.
- The results of genetic analyses may be reported in the CSR or in a separate study summary.
- The sponsor will store the DNA samples in a secure storage space with adequate measures to protect confidentiality.
- The samples will be retained while research on FMS continues but no longer than 20 years or other period as per local requirements.

10.6 Appendix 6: Liver safety – suggested actions and follow-up assessments

Study participants with PDILI must be assessed to determine if study medication must be discontinued. In addition, all concomitant medications and herbal supplements that are not medically necessary should also be discontinued.

Investigators should attempt to obtain information on study participants in the case of study medication discontinuation to complete the final evaluation.

Study participants with PDILI should not be withdrawn from the study until investigation and monitoring are complete. All results of these evaluations and observations, as well as the reason(s) for study medication discontinuation and/or study participant withdrawal (if applicable), must be recorded in the source documents. The eCRF must document the primary reason for discontinuation of study medication.

A specific monitoring plan must be agreed between the UCB study physician and the investigator for study participants who have ALT >3xULN. The monitoring plan should include any necessary follow-up assessments (until resolution of the abnormal laboratory values).

Phase 2 liver chemistry stopping criteria are designed to assure study participant safety and to evaluate liver event etiology. They are presented in the tables below.

Table 10-2: Phase 2 liver chemistry stopping criteria and follow-up assessments

Liver chemistry stopping criteria	
ALT-absolute	ALT \geq 5x ULN
ALT increase	ALT \geq 3xULN persists for \geq 4 weeks
Bilirubin^{a,b}	ALT \geq 3xULN and bilirubin \geq 2xULN ($>35\%$ direct bilirubin)
INR^b	ALT \geq 3xULN and INR >1.5 , if INR measured
Cannot monitor	ALT \geq 3xULN and cannot be monitored weekly for 4 weeks
Symptomatic^c	ALT \geq 3xULN associated with symptoms (new or worsening) believed to be related to liver injury or hypersensitivity
Suggested actions and follow-up assessments	
Actions	

Immediately discontinue study medication.Report the event to UCB within 24 hours.Complete the liver event CRF, and complete an SAE data collection tool if the event also met the criteria for an SAE.^bPerform liver chemistry follow-up assessments.	
Follow-up assessments	

Viral hepatitis serology^dObtain INR and recheck with each liver chemistry assessment until the transaminase values show downward trendObtain blood sample for PK analysis as soon as feasible after the most recent dose^e	

Table 10-2: Phase 2 liver chemistry stopping criteria and follow-up assessments

Liver chemistry stopping criteria	

 Monitor the study participant until liver chemistry test abnormalities resolve, stabilize, or return to Baseline (see MONITORING). Do not restart/rechallenge study participant with study medication. Permanently discontinue study medication, and continue study participant in the study for any protocol-specified follow-up assessments Consider the need for a toxicology screening 
MONITORING:
 
If ALT $\geq 3 \times \text{ULN}$ AND bilirubin $\geq 2 \times \text{ULN}$ or INR > 1.5:
 
 Repeat liver chemistry tests (include ALT, AST, ALP, bilirubin) and perform liver event follow-up assessments within 24 hours. Monitor study participant twice weekly until liver chemistry test abnormalities resolve, stabilize, or return to Baseline. A specialist or hepatology consultation is recommended. 
If ALT $\geq 3 \times \text{ULN}$ AND bilirubin $< 2 \times \text{ULN}$ and INR ≤ 1.5:
 
 Repeat liver chemistry tests (include ALT, AST, ALP, bilirubin) and perform liver chemistry follow-up assessments within 24 to 72 hours. Monitor study participants weekly until liver chemistry abnormalities resolve, stabilize, or return to Baseline. 	
 Serum CPK and LDH Fractionate bilirubin, if total bilirubin $\geq 2 \times \text{ULN}$ Obtain complete blood count with differential to assess eosinophilia Record the appearance or worsening of clinical symptoms of liver injury (eg, fatigue, nausea, vomiting, right upper quadrant pain), or hypersensitivity, on the AE eCRF Record use of concomitant medications (including acetaminophen [or paracetamol], herbal remedies, and other over-the-counter medications) on the concomitant medications eCRF. Record alcohol use on the liver event alcohol intake eCRF Exclude pregnancy 
If ALT $\geq 3 \times \text{ULN}$ AND bilirubin $\geq 2 \times \text{ULN}$ or INR > 1.5:
 
 Anti-nuclear antibody, anti-smooth muscle antibody, Type 1 anti-liver kidney microsomal antibodies, and quantitative total IgG or gamma globulins. Serum acetaminophen adduct HPLC assay (quantifies potential acetaminophen contribution to liver injury in study participants with definite or likely acetaminophen use in the preceding week [James et al, 2009]). Liver imaging (ultrasound, magnetic resonance, or computerized tomography) and/or liver biopsy to evaluate liver disease; complete liver imaging and/or liver biopsy CRFs.

AE=adverse event; ALP=alkaline phosphatase; ALT=alanine aminotransferase; AST=aspartate aminotransferase; CPK=creatine phosphokinase; CRF=case report form; HBsAg=hepatitis B surface antigen; HBCAb=hepatitis B core antibody; HPLC=high performance liquid chromatography; IgG=immunoglobulin G; IgM=immunoglobulin M; INR=international normalized ratio; LDH=lactate dehydrogenase; PK=pharmacokinetic; SAE=serious adverse event; ULN=upper limit of normal

^a Serum bilirubin fractionation should be performed if testing is available. If serum bilirubin fractionation is not immediately available, discontinue study medication if ALT $\geq 3 \times \text{ULN}$ and bilirubin $\geq 2 \times \text{ULN}$. Additionally, if

Table 10-2: Phase 2 liver chemistry stopping criteria and follow-up assessments

Liver chemistry stopping criteria
serum bilirubin fractionation testing is unavailable, record the absence/presence of detectable urinary bilirubin on dipstick which is indicative of direct bilirubin elevations suggesting liver injury.
^b All events of ALT $\geq 3\times$ ULN and bilirubin $\geq 2\times$ ULN ($>35\%$ direct bilirubin) or ALT $\geq 3\times$ ULN and INR >1.5 may indicate severe liver injury (possible 'Hy's Law') and must be reported as an SAE (excluding studies of hepatic impairment or cirrhosis) . The INR measurement is not required and the stated threshold value will not apply to study participants receiving anticoagulants.
^c New or worsening symptoms believed to be related to liver injury (such as fatigue, nausea, vomiting, right upper quadrant pain or tenderness, or jaundice) or hypersensitivity (such as fever, rash or eosinophilia).
^d Includes: hepatitis A IgM antibody; HBsAg and HBcAb; hepatitis C RNA; cytomegalovirus IgM antibody; Epstein-Barr viral capsid antigen IgM antibody (or if unavailable, heterophile antibody or monospot testing); and hepatitis E IgM antibody.
^e PK sample may not be required for study participants known to be receiving placebo or non-comparator interventions. Record the date/time of the PK blood sample draw and the date/time of the dose of study medication prior to the blood sample draw on the CRF. If the date or time of the last dose is unclear, provide the study participant's best approximation. If the date/time of the last dose cannot be approximated OR a PK sample cannot be collected in the time period indicated above, do not obtain a PK sample. Instructions for sample handling and shipping are in the IMP Handling Manual.

Table 10-3: Phase 2 liver chemistry increased monitoring criterion with continued study medication

Liver chemistry increased monitoring criterion and follow-up	
Criterion	Actions
ALT $\geq 3\times$ ULN and $<5\times$ ULN and bilirubin $<2\times$ ULN, without symptoms believed to be related to liver injury or hypersensitivity, and who can be monitored weekly for 4 weeks	
 Notify the UCB medical monitor within 24 hours of learning of the abnormality to discuss study participant safety. Study participant can continue study medication. Study participant must return weekly for repeat liver chemistry tests (ALT, AST, ALP, bilirubin) until the abnormalities resolve, stabilize or return to Baseline. If at any time, the study participant meets liver chemistry stopping criteria, proceed as described in Section 7.1.1. If, after 4 weeks of monitoring, ALT $<3\times$ULN and bilirubin $<2\times$ULN, monitor study participants twice monthly until liver chemistry tests resolve, stabilize, or return to Baseline.

ALP=alkaline phosphatase; ALT=alanine aminotransferase; AST=aspartate aminotransferase; ULN=upper limit of normal

10.7 Appendix 7: Medical device AEs, adverse device effects, SAEs, and device deficiencies: Definition and procedures for recording, evaluating, follow-up, and reporting

Not applicable.

This document cannot be used to support any marketing application and any extensions or variations thereof.
PUBLIC COPY

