23. Study participant has current treatment with prednisolone or equivalent (except for a short course to treat, for example, an episode of asthma or chronic obstructive pulmonary disease exacerbation).
24. Study participant has current treatment with morphine or equivalent of >80mg/day (>40mg/day if morphine or equivalent are taken in association with gabapentin [>1200mg/day] or pregabalin [>150mg/day]).
- 25a. Study participant has received a live vaccination within 4 weeks prior to Visit 1 or intends to have a live vaccination during the study or within 8 weeks following the final dose of IMP (Visit 28).

Prior/Concurrent clinical study experience

26. Study participant has previously been randomized in this study (rescreening for screen-failed participants is allowed with prior consultation and permission of the medical monitor/study physician; see Section 5.4).
27. Study participant has participated in another study of an IMP (and/or an investigational device) within the previous 30 days or 5 half-lives prior to screening (whichever is longer) or is currently participating in another study of an IMP (and/or an investigational device).

Diagnostic assessments

28. Study participant has alanine transaminase (ALT), aspartate aminotransferase (AST), or alkaline phosphatase (ALP) that is >2x upper limit of normal (ULN).
 - If study participant has >ULN for ALT, AST, or ALP that does not meet the exclusion limit at Screening, the tests must be repeated prior to dosing to ensure there was no further ongoing clinically relevant increase. In case of a clinically relevant increase as per the investigator's judgment, the study participant must be excluded.
 - Tests that result in ALT, AST, or ALP up to 25% above the exclusion limit (>2xULN) may be repeated once for confirmation. This includes rescreening. If any of the repeated tests (ALT, AST, or ALP) are >2xULN, the study participant will meet the exclusion criterion #28 and the study participant must be excluded.

- For randomized study participants with a Baseline result >ULN for ALT, AST, ALP, or total bilirubin but <1.5xULN, a Baseline diagnosis and/or the cause of any clinically meaningful elevation will have to be understood and recorded in the electronic case report form (eCRF).

29. Study participant has bilirubin >1.5xULN (isolated bilirubin >1.5xULN is acceptable if bilirubin is fractionated and direct bilirubin <35%).

30a. Study participant has IgG \leq 5.5g/L at the Screening Visit.

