7.1.2 Other permanent discontinuation criteria

Study participants **must permanently discontinue** IMP if any of the following events occur:

1. Study participant develops an illness that would interfere with their continued participation.
2. Study participant has a significant infective episode including but not limited to bacteremia/sepsis, infectious meningitis, septic arthritis, osteomyelitis, complicated pneumonia, or visceral abscess which may or may not result in hospitalization. This list is not intended to be all inclusive, and the investigator is expected to apply their clinical judgment on continuing IMP based on the clinical situation (see Appendix 14; Section 10.14).
3. Study participant has an AE of severe or serious hypersensitivity, infusion-related reaction (Appendix 15; Section 10.15), or anaphylaxis requiring corticosteroid and/or epinephrine therapy (Sampson et al, 2006).
4. Study participant has a recurrence of aseptic meningitis (see also Appendix 13; Section 10.13).

5. Participant meets PDILI permanent discontinuation criteria (see Appendix 6, Section 10.6).
6. Study participant for whom further examinations result in a diagnosis of active TB, or if the study participant is diagnosed with LTBI with no initiation of TB preventive therapy, prematurely discontinues TB preventive therapy, or, in the opinion of the investigator or sponsor is noncompliant with TB preventive therapy. An EW visit must be scheduled as soon as possible, but not later than the next regular visit.
7. Study participant has new onset or recurrent neoplastic disease (except for superficial basal or squamous cell carcinoma of the skin not requiring targeted biological therapy, chemotherapy, or radiation).
8. Study participant has active suicidal ideation as indicated by a positive response (Yes) to either Question 4 or Question 5 of the “Since Last Visit” version of the C-SSRS. The study participant should be referred immediately to a mental healthcare professional and must be withdrawn from the study.

7.1.3 Level of follow up to be considered when permanent discontinuation from IMP occurs

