8.3.6 Adverse events of special interest

An AE of special interest (AESI) is any AE that a regulatory authority has mandated be reported on an expedited basis, regardless of the seriousness, expectedness, or relatedness of the AE to the administration of a UCB product/compound.

For rozanolixizumab, the following events require immediate reporting (within 24 hours regardless of seriousness) to UCB:

- Hy's Law
 - Potential Hy's Law, defined as $\geq 3x$ ULN ALT or AST with coexisting $\geq 2x$ ULN total bilirubin (35% direct bilirubin) in the absence of $\geq 2x$ ULN ALP, with no alternative explanation for the biochemical abnormality (ie, without waiting for any additional etiologic investigations to have been concluded). Follow-up information should be reported if an alternative etiology is identified during investigation and monitoring of the study participant.

This AESI will follow the SAE recording and reporting procedures as indicated in Appendix 3 (Section 10.3).

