INR=international normalized ratio; RBC=red blood cell; SAE=serious adverse event; TB=tuberculosis;

ULN=upper limit of normal; WBC=white blood cell; WOCBP=woman of childbearing potential

The results of each test must be entered into the eCRF.

^a Details of liver chemistry stopping criteria and required actions and follow-up assessments after liver stopping or monitoring event are given in Section 10.6 (Appendix 6). All events of ALT $\geq 3 \times$ ULN and bilirubin $\geq 2 \times$ ULN ($>35\%$ direct bilirubin) or ALT $\geq 3 \times$ ULN and INR > 1.5 , if INR measured, may indicate severe liver injury (possible Hy's Law) and must be reported as an SAE (excluding studies of hepatic impairment or cirrhosis).

^b The results of these assessments will not be reported to investigative sites or other blinded personnel until the study has been unblinded, unless a safety alert requires a clinical review of the study participant.

^c Urine testing will be standard for the protocol unless serum testing is required by local regulation or IEC.

Investigators must document their review of each laboratory safety report.

Other protocol-required laboratory assessments

Laboratory Assessments	Parameters
Other laboratory assessments	
 • Blood sampling for PK of rozanolixizumab^a • Blood sampling for DNA and RNA analysis^b • Serum complement (C3, C4), and plasma complement (C3a, C5a)^b • Total IgG^a • IgG subclasses^a • Anti-drug antibodies^a • Blood sampling for exploratory biomarker analysis^b

C3=complement component 3; C3a=complement component 3a; C4=complement component 4; C5a=complement component 5a; Ig=immunoglobulin; PK=pharmacokinetics

^a The results of these assessments will not be reported to investigative sites or other blinded personnel until the study has been unblinded, unless a safety alert prompts a clinical review of the study participant.

^b The results of these assessments will not be reported to investigative sites.

10.3 Appendix 3: Adverse events – Definitions and procedures for recording, evaluating, follow-up, and reporting

Definition of AE

AE definition

- An AE is any untoward medical occurrence in a patient or clinical study participant, temporally associated with the use of study medication, whether or not considered related to the study medication.

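### A potential Hy's Law case driven by AST alone is reported and counted, but meets no liver-chemistry criterion for mandatory stopping in the readable text, because Table 10-2 names ALT only

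*Protocol*

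**What the plan says.** **Reporting and analysis use either enzyme.** Protocol Section 8.3.6 defines potential Hy's Law by a threefold rise in either transaminase ("ULN ALT or AST with coexisting" a twofold rise in total bilirubin). ALP must be below 2×ULN and there must be no other explanation. The case goes to the sponsor within 24 hours under SAE procedures. SAP Section 5.6.4 (special-interest events) and Section 5.6.9.5 (the Hy's Law row of the liver table) also accept ALT or AST. Entry is screened on both enzymes at one limit: "Study participant has alanine transaminase (ALT), aspartate aminotransferase (AST), or alkaline phosphatase (ALP) that is >2x upper limit of normal (ULN".

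**Mandatory stopping uses ALT.** Section 7.1.2 lists, among events that require permanent discontinuation: "Participant meets PDILI permanent discontinuation criteria (see Appendix 6, Section 10.6". In Appendix 6:

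- The bilirubin row of Table 10-2 reads "ALT \geq 3xULN and bilirubin \geq 2xULN ($>35\%$ direct bilirubin".
- Footnote a covers the case without fractionation: "If serum bilirubin fractionation is not immediately available, discontinue study medication if ALT" and bilirubin reach the same limits.
- The monitoring branch and the work-up branch share one condition: "If ALT $\geq 3 \times \text{ULN}$ AND bilirubin $\geq 2 \times \text{ULN}$ or INR > 1.5".
- The other five stopping rows, Table 10-3 and the monitoring-plan line ("A specific monitoring plan must be agreed between the UCB study physician and the investigator for study participants who have ALT >3xULN") also name ALT alone.

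**Two further reporting sentences use ALT.** Table 10-2 footnote b and Appendix 2 footnote a say that ALT with raised bilirubin, or ALT with raised INR, "may indicate severe liver injury (possible Hy's Law) and must be reported as an SAE".

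**The concern.** The same clinical picture is handled differently according to which enzyme crosses 3×ULN. If ALT crosses, the participant must stop permanently, must not be rechallenged, is retested within 24 hours and is then monitored twice weekly, with an extended work-up. If only AST crosses, the event is still an expedited report and a Hy's Law count in the SAP table, but none of those actions is triggered by a stated laboratory value. Neither document gives a reason for dropping AST. What is at stake is participant safety and consistency between sites, not the efficacy estimate.

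**Working it through.** The plan gives no figure to reproduce, so the check sets the texts side by side and applies them to a case.

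| Place | Enzyme named | What it controls |
|---|---|---|
| Protocol 8.3.6 | ALT or AST | 24-hour report, SAE procedures |
| SAP 5.6.4 and 5.6.9.5 | ALT or AST | Listing, Hy's Law count |
| Table 10-2, all six stopping rows | ALT | Mandatory stop through 7.1.2 item 5 |
| Table 10-2 footnote a | ALT | Stop when bilirubin is not fractionated |
| Table 10-2, two branches for bilirubin ≥2×ULN or INR >1.5 | ALT | 24-hour retest, twice-weekly tests; extended work-up |
| Table 10-2 footnote b; Appendix 2 footnote a | ALT | SAE reporting |
| Appendix 6 monitoring-plan line | ALT | Agreed monitoring plan |

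**Illustrative case (assumed values).** AST 4×ULN, ALT 2.5×ULN, bilirubin 2.5×ULN with more than 35% direct, ALP 1.2×ULN, INR not raised, no other explanation.

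- Section 8.3.6: met. SAP 5.6.4 and the SAP Hy's Law row: met.
- Table 10-2: 0 of 6 rows met, since each needs ALT ≥3×ULN or ≥5×ULN.
- Footnotes a and b, Appendix 2 footnote a, the monitoring-plan line and Table 10-3: not met.
- With ALT at 4×ULN instead, the bilirubin row and the monitoring-plan line are both met.

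**Count of rule patterns.** Fix bilirubin ≥2×ULN, more than 35% direct, and ALP <2×ULN. ALT ≥3×ULN (yes/no) by AST ≥3×ULN (yes/no) gives 4 combinations. Removing the one with neither leaves 3: ALT only, AST only, both.

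- As printed, the bilirubin row is met in 2 of 3.
- Crossing with INR >1.5 (yes/no) gives 3 × 2 = 6 cells. The 2 AST-only cells meet neither the bilirubin row nor the INR row.
- With ALT or AST in the bilirubin row alone, 3 of 3 patterns and 6 of 6 cells are met. The INR row need not change to close this gap.

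These are counts of rules, not probabilities. The documents give no frequency for the AST-only pattern.

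**The case against.** The strongest reply is that the participant is not left unprotected, and most of it stands. Section 7.1 leaves management of adverse events to the investigator. Section 7.1.1 allows stopping in the participant's best interest. Section 7.1.2 item 1 requires a stop for an illness that would interfere with participation. Section 8 calls for immediate discussion with the sponsor. Section 8.2.5 asks for significant laboratory values to be repeated, and Section 8.3.3 follows SAEs to resolution or stabilization. Appendix 6 opens by requiring an assessment of any potential drug-induced liver injury. A reader might infer that dosing would simply continue; the documents do not support that. But all of these rest on judgment, and none is a laboratory threshold.

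Figure 7-1 is a second reply. It is not shown and its legend lists AST, so it may name AST. Section 7.1.3 groups 7.1.1 with 7.1.2 for permanent discontinuation, and Table 10-3 refers back to 7.1.1. This limits the claim to the readable text. Yet 7.1.1 asks only that stopping be considered under the figure, while the binding item points to Appendix 6. If the figure does use AST, it disagrees with Table 10-2.

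Third, a reader might treat the two ALT-only footnotes (Table 10-2 footnote b, Appendix 2 footnote a) as stopping rules or as a rival definition of Hy's Law. They are SAE-reporting sentences about what may indicate it. They admit INR without bilirubin and carry no ALP condition.

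Finally, a reader might want every ALT in Appendix 6 changed. That goes too far. An AST-plus-INR stop without raised bilirubin, or a monitoring plan for any isolated AST >3×ULN, lies outside potential Hy's Law as Section 8.3.6 defines it.

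**Conclusion.** The gap is real but narrow. An AST-driven potential Hy's Law case is reported within 24 hours and counted, yet in the readable text it meets no objective liver-chemistry criterion for mandatory permanent discontinuation. Nor does it trigger Table 10-2's rechallenge ban, 24-hour retest, twice-weekly schedule or extended work-up. One of three qualifying enzyme patterns is missed. The conclusion rests on the printed Appendix 6 text and on Section 7.1.2 item 5 making it binding; Figure 7-1 could soften it but cannot be checked. It is a low-to-moderate safety consistency correction, with no effect on how the efficacy estimand is defined.

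**What to change.** At the next amendment, write ALT or AST for the condition that pairs the enzyme with bilirubin, in six places:

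1. Table 10-2 bilirubin row.
2. Table 10-2 footnote a.
3. The monitoring branch for bilirubin ≥2×ULN.
4. The work-up branch for bilirubin ≥2×ULN.
5. The bilirubin clause of Table 10-2 footnote b.
6. The bilirubin clause of Appendix 2 footnote a.

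In items 3 and 4 one mention of ALT governs both bilirubin and INR, so split the condition: ALT or AST with bilirubin ≥2×ULN, or ALT with INR >1.5. Align Figure 7-1 with the result.

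Leave to the sponsor the INR row and INR clauses, the monitoring-plan line, the other ALT rows, the monitoring branch for lower bilirubin and INR, and Table 10-3.

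The cost is wording. AST and total and direct bilirubin are already in the central laboratory panel in Appendix 2. The downside is a rare extra mandatory stop. As with ALT now, the row would also catch cases with ALP ≥2×ULN or another cause, because Table 10-2 has no such exceptions. Treatment discontinuation is the primary intercurrent event, and later data are excluded. With 60 participants × 6 post-Baseline BPI-SF visits = 360 planned scores, one such case loses at most 6/360 = 1.7%.
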